### Hypertonic Saline Infusion

The risks associated with infusing saline in the vein are low but can include damage to the vein, blood dilution, spasm or contraction of the vein, edema, high blood pressure, excess fluid in the lungs or brain, volume overload (too much fluid in the body), and heart failure. Adverse symptoms of these conditions include local arm discomfort where the

catheter was inserted, shortness of breath, a headache, and/or fluid accumulation in the arms, legs, or lungs.

None of these adverse symptoms are expected in healthy adults. Blood pressure may increase during the hypertonic saline infusion. Therefore, hypertonic saline will not be administered if resting blood pressure on the day of testing is above 140/90 mmHg. If blood pressure goes above 170/90 mmHg, we will stop the infusion. A controlled infusion of 3% NaCl has been safely performed in our lab and other labs.

### **Furosemide**

There are several risks of infusing furosemide although the adverse reactions are uncommon. Furosemide is a widely used medication. References 1 (n=199) & 3 (n=8) below used an identical dosage that we propose (40mg). The infusion of furosemide could lead to gastrointestinal, allergic, central nervous system, blood and heart reactions. Blood pressure may decrease after the furosemide bolus. If blood pressure goes below 90/50 mmHg after furosemide is given, we will stop the study visit. Symptomatic hypotension leading to dizziness or fainting may also result. Furosemide is a diuretic and increases the urge to urinate and can make participants feel thirsty. Because of this, it is likely that participants will need to use the restroom during the MRI scan. When subjects need to use the restroom during the MRI scan, they will be asked urinate into the absorbent brief they will be wearing. This is a normal response, but it may cause a feeling of embarrassment. If participants choose to come out of the MRI scan to use the restroom, the study will be concluded because the effect of the hypertonic saline and furosemide will have worn off by the time the participant is put back into the MRI. Participants will still be compensated and allowed to proceed with the other study visits.

Pregnancy: Furosemide falls under Pregnancy Category C. At higher than maximal recommended human doses, rodent studies have shown unexplained fetal harm. There are no adequate and well-controlled studies in pregnant women. Although there are no established guidelines at this time regarding furosemide and pregnancy, participants will be informed that there is risk. If the participant may be pregnant or if the participant does not want to expose themselves to this risk, they will be excluded from participating in this study. Female subjects will only be permitted to participate upon a negative pregnancy test.

### **Furosemide infusion studies performed in other labs**

3. van Meyel JJ, Smits P, Russel FG, Gerlag PG. Diuretic efficiency of furosemide during continuous administration versus bolus injection in healthy volunteers. *Clinical Pharmacology and Therapeutics*. Apr;51(4):440-444. 1992.

Magnetic Resonance Imaging (brain structure and activation):

MRI does not use any ionization radiation and it does not use radioactivity, however, there are risks associated with MRI scans. Potential risks are listed below.

- **Metal:** The MRI scanner produces a constant strong magnetic field, which may cause any metal implants, clips, or implanted medical devices within the body to shift position or malfunction. Participants will not be allowed to participate in this study if they have any implanted metal, clips or devices. Participants will be screened to make sure that it is safe for them to enter a strong magnetic field. Participants will be asked to provide as much information as they can, for example if they had surgery in the past, so that we may decide whether it is safe for them to be a participant. Metallic objects brought into the MRI environment can become hazardous projectiles and can also interfere with the data quality. To minimize this risk, metal earrings, other piercings, necklaces and any other metal in contact with their body must be removed prior to the study. Participants must also remove all items from their pockets, including coins, electronics (including cell phones and hearing aids) and wallets. Participants must remove belts with metal buckles, and they may be asked to change into a gown that we will provide if their clothing contains significant metal, including metal underwire bras.
- **Pregnancy:** Exposure to MRI scanning might be harmful to an unborn child. Although there are no established guidelines at this time regarding MRI and pregnancy, participants will be informed that there is a possibility of a yet undiscovered pregnancy related risk. If the participant may be pregnant or if the participant does not want to expose themselves to this risk, they will be excluded from participating in this study.

- **Inner ear damage:** MRI scanning produces loud noises that can cause damage to the inner ear if appropriate hearing protection is not used. Earplugs and/or headphones will be provided to protect participant's ears.
- **Claustrophobia:** When a participant is inside the MRI scanner, the "bore" of the scanner will surround the part of their body that is being scanned. For example, if a participant was getting an MRI of their knee, the participant would be positioned so that their knee was centered in the bore of the scanner. In the case of fMRI, we are interested in brain activity, and the participant's head will be centered inside a close-fitting scanning coil positioned in the bore of the scanner. If the participant feels anxious in confined spaces, they will have the option to discontinue the study. We will have subjects try our "mock" scanner to evaluate their comfort level with the enclosed space of the magnet bore. If the participant decides to participate and begins to feel claustrophobic, they will be able to tell us via the intercom or the squeeze ball and we will discontinue the study immediately.
- **Burns:** In rare cases, contact with the MRI transmitting and receiving coil, conductive materials such as wires or other metallic objects, or skin-to-skin contact that forms conductive loops may result in excessive heating and burns during the experiment. The operators of the MRI scanner will take steps, such as using foam pads, when necessary, to minimize this risk. Tattoos with metallic inks can also potentially cause burns. In addition, please let the MRI operator know immediately if you experience any heating or burning sensations during a scan. The scanning session will be stopped as soon as the participant tells the operator.
- **Nerve or muscle stimulation.** While the scanner is operating, there is a small chance that the rapidly changing magnetic fields could cause a slight tingling sensation or a muscle twitch, usually felt in the upper arms or torso. While these sensations may be startling, they are not dangerous or a health risk, and they have no lasting consequences. The sensations should stop when the scan ends. Because these sensations may nevertheless be distracting or even possibly uncomfortable, participants will be asked to squeeze the signal bulb to alert the scanner operator if they feel tingling or muscle twitching, and we will immediately stop the scan.

Participants will then have the opportunity to choose to withdraw from the study or to continue.

- **Other Risks.** Besides the risks listed above, there are no other known risks from the magnetic field or radio waves at this time. Although functional MRI scanning has been used for more than 20 years, long-term effects are unknown.

**Seven-day diets:**

There are minimal risks associated with consuming a 7-day low salt diet and 7-day high salt diet. During the high salt diet, blood pressure may rise to higher-than-normal levels, and subjects might experience slight hand swelling, frequent urination from increased water intake, bloating, nausea and/or vomiting during the dietary salt manipulation. There is no increased risk for women regardless of phase of menstrual cycle and diets should not affect menstruation.

**7-day accelerometer, 24-hour blood pressure monitoring & urine collection:**

There are no known risks to wearing an accelerometer or continuous blood pressure monitor on the upper arm. During waking hours, blood pressures are taken every 20 minutes, while at night they are taken every 30 minutes. Minor discomfort may be experienced when the cuff inflates, and it may wake subjects during sleep. The 24-hour blood pressure cuff and 24-hour urine collection may disrupt normal daily living. There are no known risks to providing a urine sample.

**STEPS TAKEN TO MINIMIZE RISK**

**Catheter Insertion & Butterfly Needle Insertion for Blood Draw**

Standard safety precautions will be taken when drawing blood samples and placing the IV catheter and butterfly needle. To minimize the risk of infection associated with blood collection, only sterile, single use catheters and butterfly needles will be used. To minimize the risk of bruising, proper blood collection technique will be utilized.

### **Condom Catheter**

[figure not shown]
There is nothing we can do to minimize the risk of discomfort when removing the condom catheter. We will ask male participants if they have a known latex allergy. If they are allergic to latex, they will not be permitted to use the condom catheter and will have to use the absorbent brief.

### **Hypertonic Saline & Furosemide Infusion**

The risks of the hypertonic saline and furosemide infusions will be minimized by having proper medical oversight of the procedure. A registered nurse, under the supervision of a cardiologist, will administer the infusions and monitor the participant throughout the entire protocol. We are using previously established hypertonic saline and furosemide doses that have shown to be safe for research (see references above). We will not administer furosemide if blood pressure is too low (hypotensive,  $<100/60$  mmHg), if subjects are allergic to sulfa drugs (Lasix/furosemide), or if subjects have low potassium in the blood at their screening visit (hypokalemia,  $<3.5$  mmol/L). Furosemide is a diuretic and increases the urge to urinate and can make participants feel thirsty. When subjects need to use the restroom during the MRI scan, they will be asked to urinate into the absorbent brief they will be wearing. This is a normal response, but it may cause a feeling of embarrassment.

Following the conclusion of the infusion protocols, participants will be given sanitation wipes and asked to change back into their clothing and remove and dispose of the absorbent brief in the private changing room and bathroom. They will also be given water and a snack and will remain in the lab for at least 45 minutes for observation by the research nurse. We will leave the IV catheter in the arm and assess blood pressure and electrolytes during this time, to ensure the values are within clinically acceptable limits prior to the participant leaving the facility. In the unlikely case the person has symptoms, an abnormal blood pressure (e.g.,  $<90/50$  mmHg or  $>170/90$  mmHg), and/or abnormal electrolyte levels (e.g., potassium level ( $<3.5$  mmol/L), the registered nurse will determine the appropriate course of action. The course of action will be determined by our post furosemide blood pressure and potassium decision charts (Figure 3). Both decision flow

charts will be followed to determine appropriate course of action after the infusion. Subjects may be asked to remain at the MRI facility for further blood pressure and electrolyte observation (up to 2 hours after infusion). The additional blood draw (4mL) will be through the IV catheter already in place. Subjects may also be encouraged to eat a diet high in potassium for a few days if potassium is low (diet suggestions attached). In the highly unlikely case of abnormal electrolytes and symptoms, subjects may be referred to their primary care physician or sent to a local emergency department via ambulance. We do not expect any adverse effects in the well-screened subjects that will be tested as part of this protocol.

**Figure 3 Decision Charts.** Post furosemide blood pressure decision chart (left). Post furosemide potassium decision chart (right). Both decision flow charts will be followed to determine appropriate course of action after the infusion.

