### **VISIT 2: SCREENING, STAR CAMPUS (60 MINUTES)**

All participants will be screened at the Nurse Managed Primary Care Center in the Health Sciences Complex of STAR. This initial screening visit lasts approximately 1 hour and involves answering an MRI screening form and a medical history questionnaire. Additionally, nurses will assess resting blood pressure, 12-lead electrocardiogram, height and weight, and obtain a venous blood and urine sample. The blood and urine sample will assess liver and kidney function, a lipid profile (i.e., cholesterol), a complete blood count, glucose, sodium, potassium, and chloride. Approximately 2 teaspoons of blood will be sampled. Investigators will review all information. Individuals with any signs or symptoms of disease (example: history of angina, chest pain, dizziness, or shortness of breath, etc.) will be excluded. Individuals with blood work within normal limits, and a resting electrocardiogram within normal limits will be accepted into the study. The results from the screening are reviewed by the registered nurse to determine if participants qualify for the study. Participants will receive a copy of the data collected on their vital statistics. Women taking hormonal or non-hormonal contraceptives will not be excluded. Additional exclusion criteria include allergy to sulfa drugs (Lasix/furosemide), claustrophobia, low blood pressure (systolic blood pressure <100mmHg and/or diastolic blood pressure <60 mmHg), high blood pressure (defined here as systolic blood pressure >130mmHg and/or diastolic blood pressure >80 mmHg), low potassium levels in the blood (<3.5 mmol/L), a history of cancer, diabetes, or any other chronic disease; a history of any heart disease; use of tobacco or nicotine products; nursing mothers; or a body mass index less than 18.5kg/m^2 or greater than 30kg/m^2. Certain medications may also result in exclusion from participating; this will be determined by the NMPCC in consultation with the primary investigator on an individual basis. If one of the test results is abnormal, individuals will be referred to their personal provider.

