### VISITS 3 & 4: fMRI SCAN (2 hours/visit; CBBI)

Subjects will be asked to log food and water intake for the 3 days leading up to the MRI visits on the AHA Sodium Tracker. Subjects will be asked to consume a diet containing 2,300 mg of sodium each of these days. Subjects will consume their own food. Food will NOT be provided by the dietitian for the 3 days leading up to the MRI visits. Subjects will be instructed to refrain from taking over the counter medications for 48 hours, and from vigorous aerobic exercise or alcohol for 24 hours prior to MRI scans. Subjects will come into the study visit after at least a four-hour fast. The MRI studies must be completed within 3 months of the screening. If we are unable to schedule both MRI visits within 3 months of screening, subjects will be asked to come to the Cardiovascular Physiology Lab again before the MRI visit for a blood draw to check if electrolyte levels are normal. The second MRI data collection must be performed no sooner than 1 week from the first MRI data collection.

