## **STUDY POPULATION AND RECRUITMENT**

We will recruit 50 normotensive men and women (18-45 years old), from the community surrounding the University of Delaware. Our study sample will be representative of the general population, including all races/ethnicities. Our strategies will include: Nextdoor app, classifieds, flyers posted locally, and targeted social media ads using 'bump' advertisement. The study will include all healthy participants with blood pressure between 100/60 to 130/80 mmHg. Individuals will not have any chronic diseases.

Participants excluded from the study will include individuals with known cardiovascular disease, high blood pressure (defined here as systolic blood pressure >130mmHg and/or diastolic blood pressure >80 mmHg), low blood pressure (defined here as systolic blood pressure <100mmHg and/or diastolic blood pressure <60 mmHg), an

allergy to sulfa drugs (Lasix/furosemide), low potassium in the blood (hypokalemia, <3.5 mmol/L), metabolic diseases, cancer, kidney disease, a body mass index (BMI) outside of the range of 18.5 and 30 kg/m^2, nicotine product consumer, pregnant or planning to become pregnant, and other chronic diseases. Participants with any conditions which would contra-indicate MRI: implant of pacemakers or pacemaker wires; artificial heart valve; brain aneurysm surgery; middle ear implant; non-removable hearing aid or jewelry; braces; cataract surgery or lens implant; implanted mechanical or electrical device; foreign metallic objects in the body such as bullets, BBs, shrapnel, or metalwork fragments; claustrophobia; uncontrollable shaking or the inability to lie still for 1.5 hours will be excluded.

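### The potassium hold on furosemide looks only at the screening value; no same-day hold is stated, although an electrolyte sample is already drawn before each infusion

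*Combined protocol and SAP*

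**What the plan says.** Under the steps taken to minimize risk, Hypertonic Saline & Furosemide Infusion gives three reasons to withhold furosemide. One is blood pressure ("We will not administer furosemide if blood pressure is too low", with a cut-off of 100/60 mmHg). The second is sulfa allergy. The third is potassium below 3.5 mmol/L, which is tied to a date: "if subjects have low potassium in the blood at their screening visit".

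The same potassium cut-off is an exclusion in two other places. Visit 2 (Screening) lists "low potassium levels in the blood (<3.5 mmol/L", and Study Population and Recruitment lists "low potassium in the blood (hypokalemia, <3.5 mmol/L), metabolic diseases, cancer, kidney disease".

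On the age of the screening value, the section on Visits 3 & 4 says: "The MRI studies must be completed within 3 months of the screening". If both MRI visits cannot be scheduled in that window, it asks for a further blood draw to check electrolytes. It gives no potassium cut-off and no consequence.

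Catheter Insertion & Blood Sample provides for electrolytes to be measured before and after the infusion. Hypertonic Saline Infusion gives the purpose of these samples as tracking changes in sodium and osmolality.

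After the infusion, staff keep the IV in place and "assess blood pressure and electrolytes during this time, to ensure the values are within clinically acceptable limits prior to the participant leaving the facility". Further, "Subjects may be asked to remain at the MRI facility for further blood pressure and electrolyte observation (up to 2 hours after infusion". The potassium decision chart in Figure 3 is captioned as post-furosemide.

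**The concern.** A condition listed as a step to reduce the risk of a drug should be able to change whether the drug is given. This one uses the analyte, cut-off and sample that already decided enrolment, so for anyone properly in the study the answer is fixed before the MRI visit. The plan treats low potassium as a reason not to give furosemide, yet does not ask for the potassium value on the day the drug is given.

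The plan does use same-day holds elsewhere. A pregnancy test precedes each scan, and saline is withheld if resting blood pressure that day exceeds 140/90 mmHg (Risks, Hypertonic Saline Infusion). It also accepts that electrolyte results go out of date, since it asks for a new draw beyond 3 months. At stake is a furosemide bolus given to someone whose potassium is already below the plan's own threshold.

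**Working it through.** The plan states no figure on this point, so the check is mainly one of logic.

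1. **Eligibility against the dosing condition.** Correct enrolment requires screening potassium of at least 3.5 mmol/L. The dosing condition is met only if screening potassium is below 3.5 mmol/L. The two sets do not overlap, so the condition can act only on someone enrolled in error.

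2. **Where a same-day rule could be.** Each electrolyte statement in the visible text:
   - Visit 2: potassium decides eligibility.
   - Visits 3 & 4: a repeat draw only if the 3-month window is missed, with no threshold or action.
   - Catheter Insertion & Blood Sample, and Hypertonic Saline Infusion: a pre-infusion sample, used to measure change.
   - Visits 5–8 (optional diets, which some participants may do before MRI): electrolytes measured, with no link to dosing.
   - Hypertonic Saline & Furosemide Infusion, with Figure 3: potassium acted on after the dose.

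   None requires a potassium result before the bolus.

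3. **Consequence.** Take a participant with screening potassium of 3.5 mmol/L or more and same-day potassium below 3.5 mmol/L. With no sulfa allergy and acceptable blood pressure, no stated potassium rule stops the dose.

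4. **Exposure.** The recruitment target is 50 ("We will recruit 50 normotensive men and women (18-45 years old"). Each participant has two MRI visits, one with furosemide.
   - Furosemide doses: 50 × 1 = 50 at most.
   - Pre-infusion samples: 50 × 2 = 100 at most.

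5. **Illustration only.** The documents give no rate of low same-day potassium. Assume a proportion p of visits between 0.5% and 2%.
   - Doses given on a low value: 50p = 50 × 0.005 = 0.25 to 50 × 0.02 = 1.
   - Visits postponed if both MRI visits are checked: 100p = 0.5 to 2, about half of them control visits.

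6. **Room in the visit for a pre-dose result.** The visit is given as 2 hours, the scan as about 1 hour, and observation as at least 45 minutes. If the 2 hours cover all of this, 120 − 60 − 45 = 15 minutes remain, shared with forms, urine test, changing and catheter placement. Assay turnaround is not stated. Electrolytes are to be checked before the participant leaves, so a same-visit result is implied. But 45 minutes is the minimum observation and it can run to 2 hours, so 45 minutes is not an upper bound on turnaround.

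**The case against.** **The sentence is largely a recap.** Sulfa allergy, in the same sentence, also repeats an exclusion, and 100/60 mmHg is also the screening cut-off. This stands: repeating an eligibility rule is not in itself a defect. A reader might infer that the blood-pressure item is a working same-day gate and the potassium item a uniquely failed one. The text does not support that contrast, because the blood-pressure item merely lacks a date and does not say it is applied on the day. What remains is that no same-day potassium hold is stated anywhere visible.

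**Three months is a deliberate validity window.** For healthy adults aged 18–45 with normal blood work and a medication review, no document shows it to be too long. This also stands, and it limits the weight of the point. It does not explain why a sample already in hand should play no part in the decision.

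**Harm is not shown.** A reader might infer that participants are left without potassium protection, or that some will be dosed while hypokalemic. Neither follows. The plan has a nurse under cardiologist supervision, a stop rule at 90/50 mmHg, and after the dose an electrolyte check, a potassium decision chart and extendable observation. The 0.5% to 2% range is an assumption.

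**The nurse may look at the result anyway, and Figure 2 might show when it is read.** Both are possible. Figure 2 is captioned as a timeline and Figure 3 as post-furosemide charts, so a pre-dose rule there is unlikely but cannot be ruled out.

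**Checking both visits postpones control visits that carry no furosemide risk, to protect a fragile blind.** Furosemide raises the urge to urinate, so participants may guess. That is a fair cost. Still, a check at one visit only would make any postponement disclose the condition outright.

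**Conclusion.** The point holds in a limited form. The stated potassium hold uses the screening value, which repeats eligibility and may be up to 3 months old, and the visible text contains no same-day hold although the sample for one is already drawn. It is more than missing detail, because the rule names a time point at which it cannot affect dosing.

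The size is small. It concerns at most 50 single doses in screened healthy adults with monitoring afterwards, and it does not touch power or the analysis. How often a low value would be found is unknown from the documents. The conclusion assumes that the figures not shown contain no pre-dose potassium rule, and it concerns what is written, not what staff may do in practice. An amendment is worthwhile as a modest safety improvement. The documents do not support calling the plan unsafe.

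**What to change.** Amend Hypertonic Saline & Furosemide Infusion so that, at both MRI visits:

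- the pre-infusion sample is drawn at catheter placement;
- its potassium is read before scanning starts;
- furosemide is not given if potassium is below 3.5 mmol/L, and the visit is postponed.

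Apply the same check and the same postponement at the control visit, so that a postponement does not reveal the condition. Keep the screening value as an eligibility rule only. Reading the result before scanning, not during it, avoids aborted scans and leaves the interval from baseline scan to infusion unchanged.

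**Cost.** No extra blood draw is needed at a visit that goes ahead. There is a wait of up to the assay turnaround, shortened by any gap already present between catheter placement and scanning. With about 15 minutes of slack at most, a slow assay would lengthen the 2-hour visit, so the amendment should state the turnaround. A rare visit would be rescheduled, with its preparation repeated: three days of sodium-targeted eating and logging, 48 hours without over-the-counter medication, 24 hours without alcohol or vigorous exercise, a fast of at least four hours, and another catheter and blood sample. If low values are equally likely at both visits, about half of these postponements would be control visits.
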